Missing Data: Patients who refuse to return for follow-up or who cannot be located and/or do not formally withdraw consent are described as "missing data." Sites will be instructed to continue efforts to contact these patients. See Statistical Plan for more information on how missing data will be handled in the analysis.

Osteolysis: As defined in Exhibit 3: Radiographic Protocol.

Other Interventions: This category includes other surgeries the patient incurs while enrolled in the study that are seemingly unrelated to the implanted device. This would include surgeries such as cholecystectomy, appendectomy, coronary artery bypass surgery, etc.

Revision: A procedure that removes part of the original implant configuration, with or without replacement of the entire component configuration.

Removal: A procedure where the entire original system configuration is removed.

Reoperation: Any surgical procedure that does not include removal or revision, for example, drainage of a hematoma at the surgical site.

Screen Failure: A patient who is either screened but not consented, consented but not randomized or randomized but does not receive the investigational or control device.

Adverse Event (AE): Any event occurring in a study subject that, in the opinion of an M.D. or other qualified and trained medical professional, represents an untoward medical occurrence that differs in either nature, severity, or frequency from a normal post-operative finding. AEs may not have an apparent causal relationship with the device. An AE can therefore be any discrete or ongoing unfavorable and unintended sign (including an abnormal laboratory finding), symptom, or disease temporally associated with the use of a product.

Serious Adverse Event: Any untoward medical occurrence that:

- Results in death
- Is life-threatening
- Requires in-patient hospitalization* or prolongation of existing hospitalization
- Results in persistent or significant disability/incapacity
- Results in congenital anomaly/birth defect

*A planned hospitalization for a pre-existing condition, or a procedure required by the protocol, without a serious deterioration in health is not considered to be a serious adverse event.

Unanticipated Adverse Device Event: any serious adverse event that is or may possibly be related to the device other than those listed in Section C: Risk Analysis or in the institution's approved Informed Consent.

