Abbreviations:

- IRB: Institutional Review Board
- ASES: American Shoulder and Elbow Surgeons Score
- SANE: Single Assessment Numeric Evaluation
- CRF: Case Report Form

RANDOMIZATION

The randomization plan will be produced using SAS v 9.2 for Windows. The sponsor will review preoperative paperwork; Informed Consent, Historical Record, and pre-operative American Shoulder and Elbow Surgeons Score prior to enrollment in the study and approve randomization for a subject based on those criteria that are evaluated and confirmed during or prior to the pre-operative visit. Control and accountability of the humeral investigational device will be managed in accordance with Sponsor SOPs.

Randomization must not occur until the surgical procedure has commenced, and the Intraoperative assessment of inclusion/exclusion criteria is completed. Patients who have met all eligibility criteria following the intraoperative assessment, and have signed the IRB-approved informed consent will be randomly assigned to one of two treatment groups. Patients will be randomized using a 1:1 blocked randomization scheme for investigational: control devices. Bilateral patients will be randomized by shoulder. See the Statistical Analysis Plan section for a specific description of the randomization scheme.

PATIENT MANAGEMENT

Table 1 summarizes the case report forms (CRFs) required during the course of the study. All surgery and follow up case report forms are recommended to be sent to Biomet Manufacturing Corp. within 2 weeks of the patient's operative/follow-up evaluation date. All Serious Adverse Events must be sent within 24 hours of the investigator's awareness of the event.

Pre- and post-operative clinical data will be collected by trained, authorized study personnel with the exception of patient-reported outcome assessments. Exhibit 11 contains an example of the Study Signature Log that will be utilized to document authorized study personnel. Clinical and patient reported outcomes will be collected on Case Report Forms (CRFs), as summarized in Table 1. Case Report Forms or checklists/worksheets may be used as source documentation when a complete source does not otherwise exist at the site.

Table 1: Screening and Follow-Up Clinical and Radiographic Exams						
Action	Pre- Operative	Intra- Operative	6-Weeks	3-Months	1-Year	2-Years annually thereafter***
Obtain written informed consent	x					
Complete subject screening and enrollment log	x					

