A significant disability is one that causes substantial disruption to the person's normal life and activity.

The investigator or designee must complete the SAE reporting (SAE100). Then relative to the event, a Revision/Removal Form (RR 100), and/or the Withdrawal Form (WD100) form should be completed. See the Implant Retrieval and Analysis of Removed Implants section below for instructions on how to handle investigational devices that are removed from study subjects.

DISCONTINUATIONS AND REVISIONS (SUBJECT WITHDRAWAL)

It is recognized that the subject's participation in this trial is entirely voluntary, and that she/he may refuse to participate and may withdraw from participation at any time without jeopardy to any future medical care. Device Revision or Removal is also considered a withdrawal event when all components are removed, or if only the humeral stem is removed. No additional study follow-up is necessary. In the event that a patient receives a partial revision (not all components/humeral stem), a revision/removal form should be completed, but the patient should still be followed per protocol. Do not complete a withdrawal form for these patients. *Enrollment for this study is defined as receipt of either a control or an investigational device.*

Therefore:

- Subjects withdrawn from the study after receipt of either the control or investigational device will NOT be replaced.
- Randomized patients who do not ultimately receive the control or investigational device:
 - 1. *WILL* be replaced, but
 - 2. Randomization assignment will not be re-used
- *All* subject withdrawals must be documented on the Withdrawal Form (WD100).

- Includes randomized patients who do not ultimately receive the control or investigational device configurations.
- If withdrawal is due to device removal or revision, the SAE 100 form must be completed. The Revision/Removal form (RR 100) should be completed in all cases including device removal details, if known.

Copies of all Case Report Forms are included in Exhibit 4.

CONTROL OF INVESTIGATIONAL DEVICE

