Investigational components (nano humeral component) will be provided in implant loaner sets that are released from the sponsor's facility for each particular case. Biomet will not release an investigational device loaner set until a copy of the signed and completed informed consent form and pre-operative forms are received and reviewed for completeness and compliance with pre-operative patient eligibility criteria. Other components that comprise the investigational or control device configuration and are currently cleared for US market use may be included in the loaner set at the discretion of Biomet. Sites are allowed to utilize their general inventory supply of the cleared components (mini stem, humeral head, hybrid glenoids) identified in Exhibit 12-Component Listing and protocol Section D: Device Description. The inventory of all devices, with the exception of the nano humeral component, will not be tracked. Any use of a device not having a part number listed in Exhibit 12 will result in a protocol deviation.

Site representatives will be instructed to return the investigational device loaner sets after each surgery unless they have received written consent from Biomet to keep the loaner set for a surgery scheduled on the following day(s).

Investigators are required to retain records of device shipment, custody transfer, allocation and device return in accordance with 21CFR Part 812.140 (a).

IMPLANT RETRIEVAL AND ANALYSIS OF REMOVED IMPLANTS

All available explanted investigational devices must be returned to Biomet. All available retrieved study implants will be handled and analyzed according to the ASTM Standard F-561-97 (Reapproved 2003) and according to the most current version of the sponsor procedure 48-Procedure for Handling of Potentially Infectious Tissues, Explants, and Instruments (Exhibit 1)

and Procedure 52-Procedure for Analyzing Returned Explants (Exhibit 2). The address for return of the item is:

Biomet Manufacturing Attn: AT Lab/Building C/Decontamination **nano IDE Study** [name]

If there are any questions regarding the return of this device, please contact the Comprehensive[®] nano IDE study manager at [name].

PRIMARY HYPOTHESES

This study is designed to demonstrate non-inferiority of the Comprehensive® Shoulder System with nano humeral component to the control devices with respect to three co-primary endpoints at 22+ months.

CO-PRIMARY ENDPOINTS

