Balanced, blocked randomization (1:1, Investigational: Control) will be implemented. Randomization will be per shoulder, and each shoulder will count as a separate case toward the total sample size. In the event that a screen failure occurs post-randomization, randomization will not be reassigned and this shoulder will not count toward the overall sample size. Randomization will continue with the next shoulder enrolled as previously described until the minimum sample size is reached in both treatment groups. Randomization will be blocked by site, and each site will receive separate randomization plans using a predetermined block size that will remain undisclosed to the sites.

SAMPLE SIZE CALCULATION INITIAL SAMPLE SIZE CALCULATIONS AND ASSUMPTIONS

The primary objective of this study is to show that the Investigational device is non-inferior to the Control device with respect to three co-primary endpoints at 22+ months. The sample size for each endpoint was calculated, and the largest chosen as the sample size for this study. The endpoint requiring the largest sample size was Radiographic Success; therefore the sample size for this study will be the one described immediately below. For reference, the sample size for the other two endpoints is shown as well.

Radiographic Success

Non-inferiority sample size calculations were implemented in nQuery Advisor 7.0 software using a 1:1 ratio of Investigational to Control subjects. This software uses methodology as described in a text by Farrington and Manning⁵.

The sample size needed to obtain 90% power for testing for non-inferiority of the investigational device to the control device with regard to radiographic success was calculated as follows:

⁵ Farrington and Manning. "Test statistics and sample size formulae for comparative binomial trials with null hypotheses of non-zero risk difference for non-unity relative risk". *Statistics in Medicine* 9(1990) pp 1447-1454.

Definitions:

 p_I : Proportion of Radiographic success in the Investigational treatment group

 p_C : Proportion of Radiographic success in the Control treatment group.

δ: Non-inferiority margin. Lower 95% confidence bound for difference in proportions of clinically successful subjects at 22+ months (Investigational – Control) must be greater than -δ.

For a specified constant, $0 < \delta < 1$, the hypotheses of non-inferiority are:

 $H_0: \ p_I - p_C \le -\delta \ vs. \quad H_A: \ p_I - p_C > -\delta.$

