Subjects who have been randomized to the Investigational or Control group in this study comprise the All Enrolled population. The co-primary endpoints will be analyzed for the All Enrolled population and the results will be compared to the primary analyses performed on the Analysis population to determine whether the results of this analysis are consistent for both populations. For patients in the All Enrolled Population who are missing data necessary for the determination of any of the co-primary endpoints at 22+ months, data will be imputed as described below in the section "Sensitivity Analyses."

ANALYSIS POPULATION

Subjects who have been randomized to the Investigational or Control group in this study and who have complete data for a primary endpoint collected per the protocol at 22+ months or who have had a revision or removal at or before 26 Months will be included in the Analysis Population. This is the population that will be used in the primary study analysis and determination of study success. Those subjects who are missing their primary endpoint at 22+ months will be included as part of the All Enrolled population described above. Subjects with protocol deviations will be analyzed on an individual basis to determine if they will be included in the Analysis Population.

MISSING DATA AND SENSITIVITY ANALYSES

Data will be considered "missing" for a given primary endpoint if this endpoint cannot be calculated or is not available for a subject in the All Enrolled population. If the subject has had a

device failure at any point on or prior to their 22+ month outcome, they will *not* be considered as missing data for the Absence of Revision/Removal/UADE endpoint, as this endpoint is cumulative. A subject who has had a revision or removal prior to two years will be considered a radiographic failure at the 22+ month time point for purposes of the primary analysis. When possible (i.e. the subject is seen by a study investigator in a non-emergency situation and collection of the data will not cause undue burden), ASES scores will be collected for these cases before the revision is performed in order to prevent these patients from missing knee scores in the primary efficacy analyses.

Sensitivity analyses will examine the sensitivity of the results to missing values of the primary outcomes using the following analyses:

Outcome Type	Analysis Description	
Binary	Tipping Point Analysis: Missing observations are replaced with	

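### Shoulders randomised during surgery that receive neither study device are relabelled screen failures and replaced, so they drop out of the primary analysis after assignment is known.

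*Combined protocol and SAP*

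**What the plan says.** **Timing.** Section B, Randomization: "Randomization must not occur until the surgical procedure has commenced, and the Intraoperative assessment of inclusion/exclusion criteria is completed". Patients found during surgery to need a specific treatment are excluded before that point (Exclusion Criteria).

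**Status of a shoulder that gets neither device.** Study Definitions includes under screen failure a patient who is "randomized but does not receive the investigational or control device". Discontinuations and Revisions says that "Randomized patients who do not ultimately receive the control or investigational device" will be replaced without re-use of the assignment. It also requires the withdrawal form, whose scope "Includes randomized patients who do not ultimately receive the control or investigational device configurations". The SAP, Randomization Details, says that after such a screen failure "randomization will not be reassigned and this shoulder will not count toward the overall sample size".

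**Who is enrolled.** Discontinuations and Revisions: "Enrollment for this study is defined as receipt of either a control or an investigational device". The SAP, All Enrolled Population: "Subjects who have been randomized to the Investigational or Control group in this study comprise the All Enrolled population".

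**Who decides study success.** The SAP's Analysis Population consists of randomised subjects who either have complete 22+ month data for a primary endpoint or had a revision or removal by 26 months. The co-primaries are also analysed in All Enrolled, with missing data imputed, to see whether the results agree.

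**Withdrawal reasons.** The closed list that follows Secondary Endpoints allows only death, written withdrawal of consent, and revision or removal.

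**The concern.** Eligibility screening is finished when the assignment is drawn. What can still prevent implantation therefore arises, at least in part, after the surgeon knows which device was assigned. An exclusion at that stage is not protected by randomisation and may depend on outcome. Co-primary (b) counts fracture or perforation of the bone or device, and Section C lists both as possible during the operation. An event of the kind the endpoint is meant to capture could therefore take the shoulder out of the denominator, and a replacement whose implantation succeeded would be analysed instead.

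The bias favours non-inferiority only if these exclusions are commoner with nano. Section C (Risks/Benefits from the Investigational Device) makes that plausible without establishing it: it says that the stemless design may increase some implant-related risks, particularly failure of biologic fixation.

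**Working it through.** **1. The plan's own figures.** Inputs from the SAP's sample size section: one-sided α 0.05, power 90%, margin 0.10, equal success rates in the two arms.

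n per arm = (1.645 + 1.282)² × 2p(1 − p) / 0.10²

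- Radiographic success, p = 0.93: 8.564 × 2 × 0.93 × 0.07 / 0.01 = 111.5, so 112 (stated 112).
- Absence of revision/removal/UADE, p = 0.95: 8.564 × 2 × 0.95 × 0.05 / 0.01 = 81.4, so 82 (stated 82).
- Attrition: 112 / 0.85 = 131.8, so 132 per arm and 264 in total (as stated).

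The replacement rule does not change these numbers. It changes which shoulders fill them.

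**2. Following one shoulder through the rules.** It is randomised in the operating room and leaves with neither study device. It is then a screen failure (Study Definitions), is withdrawn and replaced (Discontinuations and Revisions), and is not counted (Randomization Details). It would normally have no 22+ month study data. Unless an event is recorded as a revision or removal, it fails both routes into the Analysis Population, for all three co-primaries.

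**3. Effect on the error rate.** The documents give no rate of non-receipt, so the rates here are assumptions. Let q be the proportion of an arm that is excluded, with every excluded shoulder a true failure. Set true success over all randomised shoulders at 0.95 for control and 0.85 for nano, exactly at the margin. Success among the shoulders analysed is then 0.95/(1 − q) for control and 0.85/(1 − q) for nano, using each arm's own q. With 112 analysed per arm, I enumerated the two binomials exactly and summed the probability that the planned Wald bound

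(p_I − p_C) − 1.645 √[p_I(1 − p_I)/112 + p_C(1 − p_C)/112]

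is at least −0.10.

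| Excluded failures, nano / control | Nano success among analysed | Chance of false non-inferiority |
|---|---|---|
| 0 / 0 | 0.850 | 6.0% |
| 1% / 0 | 0.859 | 9.1% |
| 2% / 0 | 0.867 | 13.6% |
| 3% / 0 | 0.876 | 19.6% |
| 2% / 1% | 0.867 | 9.4% |
| 1% / 1%, 2% / 2%, 3% / 3% | 0.859, 0.867, 0.876 | 6.0% each |

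With control success at 93% (the radiographic rate) and nano-only exclusions of 0, 1, 2 and 3%, the figures are 5.6%, 8.1%, 11.7% and 16.6%.

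**4. How many shoulders would reverse a result.** Add k uncounted failures to the nano arm.

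- Safety, 106/112 in each arm: k = 5 gives 106/117 and a bound of −0.097 (pass); k = 6 gives 106/118 and −0.106 (fail).
- Radiographic, 104/112 in each arm: k = 4 gives 104/116 and −0.093 (pass); k = 5 gives 104/117 and −0.102 (fail).
- Safety, nano three successes behind (103/112 against 106/112): the bound is −0.082 (pass). Two added failures give 103/114 and −0.1003 (a narrow fail).
- Safety, nano two successes behind (104/112): two added failures give 104/114 and −0.090 (pass).

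**The case against.** A reader might infer that intraoperative failures of nano vanish from every analysis of the co-primaries. The documents do not support that, for four reasons.

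- **All Enrolled is defined by randomisation.** Read literally, it includes these shoulders. Its imputations include missing-as-failure and a tipping-point analysis. The SAP's statement that the shoulder does not count can be read as referring only to the recruitment target. This stands, but All Enrolled does not decide study success, and it treats the outcome as missing, including under a missing-as-success analysis, where it could be scored as known.
- **A device failure is not missing for co-primary (b).** Missing Data and Sensitivity Analyses says so because the endpoint is cumulative. A failure during surgery could be counted on that reading. The text permits this without settling it.
- **The affected group is narrow.** A switch from nano to mini is receipt of a study device; it is analysed as treated, with an as-randomised sensitivity analysis. A fracture with the study implant left in place remains a failure of (b). Neither falls under the replacement rule.
- **Same-operation exchange is undefined.** One might read 'ultimately' as covering a nano that was implanted and exchanged in the same operation. The protocol also says that subjects withdrawn after receipt of a device are not replaced, and its definitions of revision and removal carry no time limit. Either classification is possible.

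It is also tempting to see a contradiction with Control of Investigational Device, which says "Any use of a device not having a part number listed in Exhibit 12 will result in a protocol deviation". One case can be both a deviation and a withdrawal, so that is not a conflict. Nor would such events necessarily go unrecorded: the operative record, adverse event, deviation and withdrawal forms are all available during surgery.

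On size, the objection is sound that inflation needs unequal exclusions, and no document gives a rate for either arm. The 2% planned for fracture or perforation of bone covers all such events. It says nothing about how many end in a non-study implant, so it does not support the 1–3% range.

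**Conclusion.** The concern holds for the primary analysis. A randomised shoulder that receives neither study device is withdrawn, replaced and, in the ordinary course, absent from the Analysis Population for all three co-primaries. The exclusion is made after assignment is known and may depend on outcome. The All Enrolled analysis limits the damage but does not remove it, and its definition conflicts with the protocol's definition of enrolment and sits uneasily with the SAP's rule on counting. The list of withdrawal reasons also omits this category.

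The size is unknown. On the assumption that 1–3% of shoulders in the nano arm only are excluded failures, false non-inferiority at the margin rises from 6.0% to between 9.1% and 19.6% on the safety endpoint. At 2% against 1% it is 9.4%; with equal exclusions there is no inflation. If observed success is equal in the two arms, five (radiographic) or six (safety) uncounted nano failures would be needed to reverse the conclusion. The direction of any bias is plausible but not shown, and the event may be rare. The case for change rests on the exclusion rule itself and on how little it costs to remove.

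**What to change.** 1. End screen failure at randomisation in Study Definitions, Discontinuations and Revisions, and the SAP's Randomization Details.
2. Keep every randomised shoulder in its randomised arm for the co-primary analyses, and keep it in follow-up. Replacements may still be enrolled to maintain the number implanted.
3. Count an intraoperative fracture or perforation of bone or device, or removal of a study component in the same operation, as a failure of co-primary (b), whatever implant is finally placed.
4. Prespecify how non-receipt scores on radiographic success and on ASES, with failure as the conservative analysis. Other scorings are defensible if fixed in advance.
5. Reconcile the definitions of enrolment and withdrawal across Discontinuations and Revisions, the list after Secondary Endpoints, Randomization Details and All Enrolled Population.

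The cost is protocol and SAP wording plus follow-up of a few extra shoulders. Nano success rates may look slightly less favourable. If the devices were otherwise equal and 2% of nano shoulders alone scored as failures this way, power at 112 per arm would fall from 90% to about 73% (radiographic) and from 96% to 82% (safety). The 2% is again an assumption.
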